### 11.2 SAMPLE SIZE DETERMINATION

This will use a Simon's two-stage design. The two-stage design to test a difference of 9.2% (2% vs. 11.2%) has an expected sample size of 30.33 and a probability of early termination of 0.787. If the pre-operative BTX injection is effective, there is a 0.124 probability of concluding that it is not, equivalently 0.876 power. After the pre-operative BTX injection on 25 patients in the first stage, the trial will be terminated if 2 or more crPOPF. If the trial goes on to the second stage, a total of 50 participants will be studied. If the total number crPOPF is less than 3, the drug will be considered efficacious. Anticipating 10% drop-out (lost follow-up), up to 55 participants need to be enrolled to achieve 50 evaluable participants. The sample size and power analysis were conducted using PASS 15 software (<http://www.ncss.com/software/pass/>).

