	Preoperative endoscopy with Sphincter of Oddi BTX injection will be the only trial-related intervention for patients participating in this trial. All the other procedures, including assessment of laboratory parameters, belong to the standard perioperative and postoperative procedures performed in patients undergoing distal pancreatectomy. In patients with childbearing potential, a pregnancy test will be performed during the routine preoperative laboratory examinations.
Statistical Analyses	This is a single arm, open-label, Phase II study to estimate the rate of clinically relevant POPF in participants that receive pre-operative endoscopic BTX injection. Using a Simon's 2-stage, a total of 50 evaluable participants will achieve an 88% power to detect a difference in crPOPF rate of 9.2% (H0: $\pi = 0.112$ versus Ha: $\pi = 0.02$ ; with a one-sided alpha level of 0.05). The trial will be continued following stage 1 if there is one or fewer crPOPF among the first 25 participants. If the study proceeds to stage 2, a total of 50 participants will be evaluated towards the primary endpoint, and the intervention considered promising if there are two or fewer cases of crPOPF.

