### 3. STUDY DESIGN

#### 3.1 DESCRIPTION OF THE STUDY DESIGN

Refer to Section 11, *Statistical Analysis* for additional information regarding statistical methods used in this study.

This is a Phase II, open-label study to estimate the rate of crPOPF in patients that receive pre-operative endoscopic BTX injection into the sphincter of Oddi as a single agent prior to undergoing distal pancreas resections. The study design consists of a single arm intervention group (n=50) with comparison to historical rates for crPOPF. BTX injection will occur 7-14 days before the planned date of surgery as an outpatient endoscopic procedure. Thereafter, participants will receive all surgery and postoperative treatment in accordance with institutional standards.

The trial will commence with the enrollment of the first six patients for a safety-run in of the endoscopic BTX injection technique. During the safety run-in, the PI will evaluate patient safety outcomes including grade 3 or higher adverse events. Additionally, the study will be evaluated by the DSMC following the completion of the first three participant's safety evaluation periods (30 days following BTX injection or 30 days following surgery, whichever is longer).

Progressive study enrollment will continue throughout the safety run-in, and enrollment will be halted if recommended by the DSMC after completion of the run-in. If 2 or more of the first 6 participants enrolled experience delay in planned surgery  $\geq$  14 days (due to significant GI hemorrhage, perforation, or adverse reaction to BTX) or pancreatitis requiring hospitalization,

then the study will be halted for safety. A total of 25 patients will be enrolled prior to a planned interim analysis for the primary endpoint of interest (crPOPF). If sufficient number of participants have experienced crPOPF (2 or greater), the trial will be prematurely terminated. If the interim analysis does not result in study termination, enrollment of the remaining participants will resume to enroll a total of 50 patients completing study intervention and follow-up.

The study schedule will be divided into 2 periods: (1) the post-treatment period which starts at the time of BTX injection and ends on the day of surgery (2) the postoperative period which begins at the time of surgery and ends 30 days postoperatively.

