#### 5.4.1 HANDLING PARTICIPANT DISCONTINUATION FROM STUDY

When a participant discontinues participation in the study, the reason the participant is no longer participating, the study name, IRB study number, and the date of discontinuation must be documented in the participant's medical record. The change in study status must be documented in the appropriate clinical trial management system (e.g., eCRIS) per OHSU policy.

For all other reasons for discontinuation from the study treatment phase, the participant should return to the clinic for the end of treatment (EOT) visit according to Section 8, STUDY PROCEDURES/EVALUATIONS AND SCHEDULE.

Participants enrolled in this study who withdraw prior to initiating their treatment will be replaced.

Participants who sign the informed consent form, receive the study intervention, and subsequently withdraw, or are withdrawn or discontinued from the study prior to undergoing planned pancreatic surgery will count towards enrollment totals

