#### 11.4.5 PLANNED INTERIM ANALYSES AND STOPPING RULE

A safety-run in to test the endoscopic BTX injection technique will be performed. During the safety run-in, the PI will evaluate patient safety outcomes including grade 3 or higher adverse events. Additionally, the study will be evaluated by the DSMC following the completion of the first three participant's safety evaluation periods (30 days following BTX injection or 30 days following surgery, whichever is longer). Progressive study enrollment will continue throughout the safety run-in, and enrollment will be halted if recommended by the DSMC after completion of the run-in. If 2 or more of the first 6 participants enrolled experience delay in planned surgery  $\geq$  14 days (due to significant GI hemorrhage, perforation, or adverse reaction to BTX) or pancreatitis requiring hospitalization, then the study will be halted for safety. If 2 or more of the first 6 participants experience delay in planned surgery  $\geq$  14 days (due to significant GI hemorrhage, perforation, or adverse reaction to BTX) or pancreatitis requiring hospitalization, the study will be halted for safety. An analysis of adverse events will be performed, and if an alteration in the intervention technique or other prophylactic treatment cannot be identified the study will be terminated. If an alteration or prophylactic treatment can be found, the study will resume with an additional 6 patient safety run-in with identical stopping rules.

A futility analysis will be conducted based on the stopping rule of Simon's two-stage design after 25 Stage I participants have met the eligibility criteria for the efficacy evaluable population (defined in 11.3.2). All participants enrolled on stage 1 (n=25) will need to complete the study intervention, distal pancreas resection, and 30 days of follow up for postoperative pancreatic fistula before the interim analysis can be completed. Recruitment will be paused until interim analysis is completed. The trial will be terminated if there are 2 or more crPOPF among these 25 participants. If there are less than 2 crCOPF among these Stage I participants, the trial will continue and enroll 25 additional participants in Stage II. The treatment will be considered promising and deserving of further investigation if there are less than 3 crCOPF among the total of evaluable 50 participants.

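### At the plan's own 10% drop-out, 55 injected participants yield 50 evaluable only about half the time once stage 2 fills, and no rule covers a shortfall

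*Combined protocol and SAP*

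**What the plan says.** **Size.** Section 11.2: "Anticipating 10% drop-out (lost follow-up), up to 55 participants need to be enrolled to achieve 50 evaluable participants". The Synopsis sets the same ceiling: up to 55 undergo the intervention so that 50 complete 30-day follow-up.

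**Who uses up a place.** At OHSU a participant is enrolled once injected (Section 5.2.1). Section 5.4.1 provides replacement for those who withdraw before treatment. Those who are injected and then leave "prior to undergoing planned pancreatic surgery will count towards enrollment totals", and Section 5.4 says the same of any withdrawal after the intervention.

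**Who is evaluable.** Under Section 11.3.2 a participant must be injected, operated on and followed for POPF. No surgery, or surgery beyond 6 weeks, removes a participant from efficacy (Sections 8.5 and 11.3.2). Missing values are not imputed (Section 11.5).

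**Counting unit.** Section 3.1 reads "A total of 25 patients will be enrolled prior to a planned interim analysis for the primary endpoint of interest (crPOPF". Section 10.7 refers to the first 25 participants without qualification, and Section 11.2 to 25 patients after injection. Section 11.4.5 places the futility analysis "after 25 Stage I participants have met the eligibility criteria for the efficacy evaluable population". If the trial passes, "the trial will continue and enroll 25 additional participants in Stage II", and the final rule is then stated for 50 evaluable participants.

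**The concern.** A planned size should deliver the number on which its decision rule is built. Here the allowance covers roughly the average loss and has no margin. It sits under a fixed ceiling, and the plan is silent on what happens if the ceiling is reached with fewer than 50 evaluable.

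The 10% is also labelled as lost follow-up only, although cancelled or late surgery removes participants too. The schematic's 28-day window for evaluability disagrees with the 6 weeks in Sections 8.5 and 11.3.2. Those passages must be reconciled, because the window affects the loss rate.

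At stake is the meaning of a promising result. With a fixed limit of two events, fewer participants make the limit easier to meet, so an ineffective treatment passes more often. If the plan does not settle this beforehand, the choice will be made after outcomes are known.

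**Working it through.** **Inputs.** Null rate 0.112 and alternative 0.02 (Section 11.2). Continue if at most 1 crPOPF in 25; promising if at most 2 in 50 (Sections 11.2 and 11.4.5). Drop-out 10% and ceiling 55 (Section 11.2, Synopsis). Losses are assumed independent of each other and of the fistula outcome.

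**1. Reproduce the plan's design figures** at 0.112 with n = 25.
- P(0 events) = 0.888^25 = 0.0513
- P(1 event) = 25 × 0.112 × 0.888^24 = 0.1618
- P(continue) = 0.0513 + 0.1618 = 0.2132, so early termination is 0.787
- Expected sample size = 25 + 25 × 0.2132 = 30.33
- Power at 0.02, by the two-stage formula in step 4, is 0.876

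All three agree with Section 11.2 ("there is a 0.124 probability of concluding that it is not, equivalently 0.876 power").

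**2. The 55.** 50 × 1.10 = 55, which matches the plan. Dividing instead gives 50/0.90 = 55.6, rounded up to 56. The difference is one participant and a matter of convention.

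**3. Yield from 55 injected.** The expected number evaluable is 55 × 0.90 = 49.5. With D ~ Binomial(55, 0.10), P(at least 50 evaluable) = P(D ≤ 5). Summing over 50 to 55 evaluable:

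0.1793 + 0.1582 + 0.1095 + 0.0558 + 0.0186 + 0.0030 = 0.524

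The chance of a shortfall is therefore 0.476. The five spare places are already included.

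| Loss rate | P(at least 50 of 55) |
|---|---|
| 5% (assumed) | 0.944 |
| 8% (assumed) | 0.724 |
| 10% (plan) | 0.524 |
| 12% (assumed) | 0.340 |
| 15% (assumed) | 0.148 |

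**4. The final rule below 50.** Keep stage 1 at 25 evaluable and let n be the total evaluable.

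P(promising) = P(0 in 25) × P(≤ 2 in n − 25) + P(1 in 25) × P(≤ 1 in n − 25)

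At n = 50 and 0.112, P(≤ 2 in 25) = 0.4581, so the result is 0.0513 × 0.4581 + 0.1618 × 0.2132 = 0.058.

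| n evaluable | P(promising) at 11.2% | P(promising) at 2% (power) |
|---|---|---|
| 50 | 0.058 | 0.876 |
| 49 | 0.063 | 0.879 |
| 48 | 0.068 | 0.881 |
| 47 | 0.073 | 0.884 |
| 46 | 0.078 | 0.886 |
| 45 | 0.084 | 0.889 |

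**5. Average effect at 10% loss.** Given a shortfall, the mean number evaluable is 47.6 and the mean error is 0.070. Overall, with the analysis held at 50 when more are evaluable, the error is 0.524 × 0.058 + 0.476 × 0.070 = 0.064. The rise is about 0.006. Average power is 0.879.

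**6. How often a shortfall arises at all.** At 11.2% the trial must first continue: 0.213 × 0.476 = 0.10. At 2%, early stopping has probability 0.089, so 0.911 × 0.476 = 0.43.

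**The case against.** Much of the opposing case stands.

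**Counting unit.** A reader of Section 3.1 alone might infer that stage 1 closes at 25 injected, with fewer than 25 evaluable. The documents do not support that. Section 3.1 refers to Section 11 for methods and itself aims for 50 who complete intervention and follow-up. Section 10.7 applies its rule by reference to Section 11.4.5, which holds the analysis until 25 have completed injection, resection and 30 days of follow-up. What remains is wording that does not match the governing section.

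**Replacement.** Section 5.4.1 might be read as barring any replacement of injected participants who are lost. It says only that they count to the total. That total allows 55 for 50, so up to five can be made up.

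**The 52%.** This is not the chance that the trial as a whole falls on one side or the other. It applies once stage 2 fills all 55 places, and it depends on the 10% planning figure.

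**Size.** The average rise in error is about 0.006. The 0.084 at 45 is a tail value, since 45 or fewer evaluable has probability 0.044. Most of the gap to the Synopsis figure ("with a one-sided alpha level of 0.05") is already present at n = 50. That is a separate matter and adds nothing here.

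**Procedure.** Nowhere does the plan say that the limit will be applied unchanged below 50; it is silent. The exact interval in Section 11.4.1 remains valid at any attained number.

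The objection leaves two things unanswered: the stated 55 does not reliably deliver 50 at the plan's own rate, and no rule is given for when it does not.

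**Conclusion.** The point holds and is minor. Under a ceiling of 55 injected and 10% loss, the expected yield is 49.5, and the chance of 50 evaluable is about 52% if stage 2 fills. If the limit of two events is then used on fewer than 50, P(promising) at 11.2% goes from 0.058 to between 0.063 and 0.084 for 49 down to 45 evaluable, and averages about 0.064. Power does not fall, so the only loss is in protection against a false positive.

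This rests on independent losses at 10%, stage 1 counted as 25 evaluable as Section 11.4.5 requires, and an unchanged final limit. The last of these is an assumption made where the plan is silent. If cancelled or late surgery takes the total loss above 10%, the chance of reaching 50 is lower. If the total loss is nearer 5%, the problem largely disappears.

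**What to change.** 1. In Sections 3.1, 10.7 and 11.2, and in the Section 11.4.5 sentence on enrolling 25 more, define both stages as the first 25 and the first 50 efficacy-evaluable participants in order of injection.
2. In Section 5.4.1, say that injected but non-evaluable participants stay in the safety population and count to the ceiling of 55, but do not fill a place in the two-stage count.
3. In Section 11.2, state that 55 injected gives an expected 49.5 evaluable and about a 52% chance of 50 at 10% loss. Say whether the 10% covers cancelled and late surgery as well as loss to follow-up.
4. In Section 11.4.5, pre-specify that if the ceiling is reached with fewer than 50 evaluable, the decision is reported with the exact error of the rule at the attained number, using the step 4 table.

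The cost is wording and one small table, with no added participants; the stated figures become slightly less favourable. These changes disclose the 52% but do not raise it. If the sponsor wants firmer assurance, a ceiling of 59 or 60 injected would give 50 evaluable with probability 0.933 or 0.966 at 10% loss. That would mean four or five more injections and less room under the limit of 64 consented.

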### 11.3 POPULATIONS FOR ANALYSES

#### 11.3.1 Safety Population

The safety population includes all enrolled participants who received the single BTX injection. All safety analyses related to the intervention will be conducted using the population receiving BTX injection. Analysis for demographics, baseline characteristics, disease history, on-study treatment summaries, concomitant medications, and participant disposition will also be conducted using the safety population.

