## 1.3 RISK/BENEFIT ASSESSMENT

### 1.3.1 KNOWN POTENTIAL RISKS

Botulinum toxin (onabotulinumtoxinA; Botox) has been used for decades with great efficacy in multiple conditions. BTX has an excellent safety profile, with one systemic review of 36 randomized controlled trials noting no serious adverse events, with focal weakness at/around the injection site being the only mild-moderate adverse event that occurred more often than controls, which is not a relevant risk for endoscopic injection. Post-marketing reports indicate that the effects of all botulinum toxin products may spread from the area of injection to produce symptoms consistent with botulinum toxin effects. These may include asthenia, generalized muscle weakness, diplopia, ptosis, dysphagia, dysphonia, dysarthria, urinary incontinence and breathing difficulties, depending on the site of injection. These symptoms have been reported hours to weeks after injection. Swallowing and breathing difficulties can be life threatening and there have been reports of death. The risk of symptoms is probably greatest in children treated for spasticity but symptoms can also occur in adults treated for spasticity and other conditions, particularly in those patients who have underlying conditions that would predispose them to these symptoms. In unapproved uses, including spasticity in children, and in approved indications, cases of spread of effect have been reported at doses comparable to those used to treat cervical dystonia and at lower doses.

In cases of endoscopic BTX injection, side-effects apart from asymptomatic serum lipase elevations or mild pancreatitis have not been previously reported when administered for Sphincter of Oddi dysfunction, post-cholecystectomy biliary pain, or for prevention of POPF.

Risks specific to endoscopy represent additional study-related risks, and include postinterventional pancreatitis defined by the Atlanta criteria which includes two of the following: 1) abdominal pain consistent with acute pancreatitis; 2) serum lipase  $> 3$  ULN; 3) characteristic imaging findings). Rare risks with the upper endoscopy procedure include cardiopulmonary compromise with procedural sedation, intraprocedural hemorrhage, and bowel perforation.

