### 5.2.1 ENROLLMENT PROCEDURES FOR THE OHSU SITE

Eligibility must be confirmed and documented by the Principal Investigator prior to enrollment.

Materials required to complete the eligibility review include, at minimum:

- Current IRB-approved consent form and HIPAA Authorization for the study signed & dated by the participant
- Documented (signed and dated) attestation by the PI confirming participant's eligibility based on available source documentation and authorizing enrollment
- Endoscopic evaluation at the time of planned study intervention to verify anatomic eligibility for BTX injection

Once eligibility is confirmed, the participant is considered 'enrolled' once study intervention is performed.

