## **8.3 SCREENING ASSESSMENTS**

A screening (consultation) visit may occur as part of standard of care. If a participant is eligible for the study after review of key inclusion/exclusion criteria, additional screening visits will be scheduled while staff members are requesting insurance authorization to participate in a clinical trial.

The following will be reviewed at screening visit:

- Clinical history and physical exam (per standard of care)
- Informed consent obtained and documented

Toxicities which occur prior to the start of treatment will not be subject to analysis. Consent must be obtained before initiation of any clinical screening procedure that are performed solely for the purpose of determining eligibility for this research study. Evaluations performed as part of routine care before informed consent can be utilized as screening evaluations if done within the defined time period.

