## **8.4 EARLY TERMINATION OR END OF STUDY VISIT**

Any participant who undergoes early termination will undergo end of study visits depending on their progress in the protocol. Participants who have not received BTX injection are not considered enrolled, will not require a follow up visit and will be treated per standard of care.

Participants who have received injection but not yet had surgery will have a follow-up visit within 30 days of intervention to evaluate for adverse events. Participants undergoing termination following pancreatectomy will have an end of study visit at the time of their regular post-op visit and will be cared for per the standard of care.

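### A study endoscopy that ends without injection falls outside the safety population, the SAE rate and the run-in count, although its risks are study-related

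*Combined protocol and SAP*

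**What the plan says.** The Synopsis describes endoscopy with injection as the only trial-related intervention, and section 1.3.1 says: "Risks specific to endoscopy represent additional study-related risks".

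At the main site, one item of the eligibility review is: "Endoscopic evaluation at the time of planned study intervention to verify anatomic eligibility for BTX injection" (5.2.1). The same section adds that "the participant is considered 'enrolled' once study intervention is performed". The plan therefore foresees a study endoscopy that ends without injection. For that participant:

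- Screening has not ended, because 5.1.1 closes it when the injection is initiated.
- Section 5.3 makes them a screen failure, not counted towards planned enrolment. Any SAE belongs to the minimal screen-failure data.
- Section 8.4: "Participants who have not received BTX injection are not considered enrolled, will not require a follow up visit".
- Section 8.3: "Toxicities which occur prior to the start of treatment will not be subject to analysis". Sections 8.1.5 and 10.5 start AE monitoring and recording at treatment.
- Section 11.3.1: "The safety population includes all enrolled participants who received the single BTX injection", and "All safety analyses related to the intervention will be conducted using the population receiving BTX injection". Section 11.4.2.1 computes the SAE rate in that set.
- The run-in rule in 11.4.5 (also in 3.1) reads: "If 2 or more of the first 6 participants enrolled experience delay in planned surgery" of at least 14 days from listed causes, or pancreatitis requiring hospitalization, the study is halted.

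**The concern.** The safety endpoint in 2.2 includes gastrointestinal hemorrhage, perforation and events that delay or prevent surgery. An endoscopy can cause each of these without any injection, in a person who was scoped only because of the trial. A bleed or perforation before the needle goes in is also a reason to abandon the injection. In that case the event itself removes the participant from both numerator and denominator of the SAE rate, and from the run-in count.

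Two things are at stake. The reported SAE rate may be incomplete for the procedure that participants actually accept. And a run-in meant to test the injection technique would leave out attempts at which the technique could not be completed. Without a follow-up visit, a delayed event such as pancreatitis may not be found at all. Grade 3 or higher events that are not serious are not part of the screen-failure data.

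**Working it through.** The plan gives no figure for this point, so the check compares definitions and then sizes the gap.

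**Inputs**
- At most 64 consented and at most 55 receiving the intervention (Synopsis).
- 163 adverse events in 73,029 endoscopic procedures (Table 3): 163/73029 = 0.22%, matching the table's total row.
- Run-in trigger: 2 or more of the first 6 (11.4.5).
- *m* = number of study endoscopies ending without injection. The documents do not give it. The planned totals allow 0 to 64 − 55 = 9. That gap also has to absorb ordinary eligibility failures and withdrawals before endoscopy, so 9 is a ceiling.

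**Step 1. Does any provision bring the participant back into the analysis?**
- 5.3 records an SAE but assigns it no analysis.
- 10.2.1 counts AEs generally from consent, but 8.1.5, 8.3 and 10.5 set the collection and analysis window at treatment. This adds a contradiction and does not close the gap.
- The Synopsis wording could let the study intervention begin with the endoscopy, but 8.4 and 11.3.1 require the injection.
- 5.2.2 enrols sub-site participants at eligibility confirmation, before the intervention. Sub-sites open only after a protocol modification (4.4), and 11.3.1 would still exclude anyone not injected.
- 10.7 and the repeated run-in sentence in 11.4.5 omit the word enrolled; 3.1 and the first sentence in 11.4.5 include it. The count is therefore ambiguous, and the fuller wording excludes the participant.

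**Step 2. Effect on the SAE rate if an event occurs** (exact Clopper-Pearson 95% intervals, no SAE among the injected)

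| Set | SAEs/n | Rate | 95% CI |
|---|---|---|---|
| Injected only, as planned | 0/55 | 0% | 0 to 6.5% |
| All scoped, *m* = 1 | 1/56 | 1.8% | 0.05 to 9.6% |
| All scoped, *m* = 3 | 1/58 | 1.7% | 0.04 to 9.2% |
| All scoped, *m* = 9 | 1/64 | 1.6% | 0.04 to 8.4% |

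**Step 3. How likely is such an event?** P(at least one) = 1 − (1 − q)^*m*.

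| Event rate q | *m* = 1 | *m* = 9 |
|---|---|---|
| 0.22% (Table 3) | 0.2% | 2.0% |
| 1% (assumed) | 1.0% | 8.6% |
| 5% (assumed) | 5% | 37% |

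Table 3 covers endoscopy in general and all listed events, so 0.22% is only a guide. The formula also treats a complication and a missed injection as unrelated. Where the complication is the reason for stopping, the rate among these endoscopies is higher, which is why the assumed rates are shown.

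**Step 4. Run-in.** With event risk p per participant, P(2 or more of 6) = 1 − (1 − p)^6 − 6p(1 − p)^5. This gives 0.007% at p = 0.22%, 3.3% at 5% and 11.4% at 10%. Because two events suffice, one uncounted event can decide the outcome: one qualifying event among six injected participants, plus one at an endoscopy without injection, counts as 1 of 6.

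**The case against.** The strongest reply is that the plan answers the question it asks. Section 2.2 words the objective as the safety of the injection, and the endpoint as events following injection. A set of injected participants fits that wording. This stands as a description of the stated endpoint. It does not explain why risks that 1.3.1 calls study-related have no place in any safety analysis.

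A reader might infer that the SAE rate is biased downward as a matter of course. The documents do not support that. The rate is too low only if a participant without injection has an event. Adding event-free participants lowers it: 2/55 = 3.6% becomes 2/64 = 3.1%.

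A reader might also infer that these events go unseen. They need not. Section 5.3 collects SAEs in screen failures for transparent reporting. Section 10.2.2 makes a procedure-related complication that delays surgery an SAE without requiring injection. Sections 10.2.3 and 10.6.1 cover research-related problems and IRB reporting. Section 10.7 can pause the study for certain grade 4 toxicities, and under 12.1 the DSMC can suspend or terminate. What is missing is the tabulated rate, the 2-of-6 count and active follow-up.

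Finally, it is tempting to let participants without injection fill places among the first six. That would weaken the run-in. If two of six were not injected and had no event (an assumption), then at a 10% risk the trigger probability falls from 11.4% to P(2 or more of 4) = 1 − 0.9^4 − 4(0.1)(0.9^3) = 5.2%. This objection stands and shapes the fix. So does the limit on what the rule counts: a sedation-related arrest is not among the causes listed in 11.4.5.

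**Conclusion.** The gap is real and definitional. The plan foresees a study endoscopy without injection and assigns that participant to no safety analysis, no follow-up visit and, on the fuller wording, no place in the run-in count. If a procedural complication stops the injection, the reported result could be 0/55 with an upper limit of 6.5%, where all endoscopies started would give 1/56 to 1/64 with upper limits of 9.6% to 8.4%.

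The expected impact is small. The number affected is unknown and at most 9, assuming the Synopsis totals are reached. At the Table 3 rate, the chance of any such event is 0.2% to 2.0%. The primary endpoint and the two-stage efficacy decision are unaffected. The sponsor should correct it, ideally before any such case arises, so that the choice of set is not made with the events known.

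**What to change.** 1. In 11.3.1, define a procedural safety set: all participants in whom sedation for the study endoscopy was started, whether or not BTX was injected.
2. Collect AEs from that point, and make a 30-day contact with participants who were not injected.
3. Report the 11.4.2.1 SAE rate in this set with the injected-only rate alongside, and word the 2.2 endpoint to match.
4. For the run-in, keep six injected participants as the denominator. Count any qualifying event at a study endoscopy without injection that occurs during the run-in towards the existing trigger of two.
5. Reconcile 5.1.1, 8.1.5, 8.3, 8.4, 10.2.1, 10.5, 10.7, 11.3.1 and 11.4.5. Settle what enrolled means, since 5.2.1 and 5.2.2 differ and 11.4.5 uses the word in one run-in sentence but not in its repetition.
6. Leave the efficacy-evaluable set in 11.3.2 unchanged.

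The cost is protocol wording and one contact for a few extra participants. The reported SAE rate may be slightly less favourable, or slightly diluted by participants who were not injected; showing the injected-only rate alongside makes either effect visible.
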